Improving Pulmonary Function Following Radiation Therapy
NCT02843568

PI: [name]
Version Date: 6/9/2022

UW16037 Improving Pulmonary Function Following Radiation Therapy

Principal Investigator: [name], DABR, FAAPM
Director, Radiation Oncology Physics
Department of Human Oncology
University of Wisconsin Madison
Office: [contact]
[contact]

Co-Investigators:

[name]	[name]
[name]	[name]
[name]	[name]
[name]	[name]
[name]	[name]
[name]	
Collaborator [name], PhD	[name]
[name].	

Biostatistician: [name]
Professor
Depts. of Statistics and of Biostatistics & Medical Informatics

Data Manager: [name]
Clinical Coordinator
Department of Human Oncology
[contact]
[contact]

Improving Pulmonary Function Following Radiation Therapy

SCHEMA

All patients	Pre-RT 4DCT scans
All patients	Pre-RT weight, labs, morbidity scores, and PFTs

S T R A T I F Y	
Conventional Fractionation
 
60* subjects
 
(A total of 60-66 Gy, in daily fractions of 1.8-2.0 Gy/fx, nominally 5 fx/week)
 
Hypo-fractionation
 
60* subjects
 
Stereotactic body radiation therapy (40-60 Gy total, in 3-8 fx, using standard schemes at UWHCC) or 12Gy x 4 fx, 10Gy x 5 fx, 5Gy x 8 fx, or 20Gy x 3 fx
 
*To achieve primary objective, subjects must complete 3 month post RT assessments. If this does not occur, the subject will be replaced.
	R A N D O M I Z E	
Arm 1:
 
Create treatment plan that meets standard dose specifications
 
Arm 2:
 
Optimize treatment plan meet standard dose specifications and to minimize pulmonary function damage based on predictive model

1. OBJECTIVES

1.1. Primary Objective

This clinical trial sets out to determine if subjects who have been treated with radiation therapy plans designed to spare high ventilation regions have superior preservation of pulmonary function compared to those treated with standard radiation dose distributions. Four dimensional computed tomographic imaging (4DCT) will be used to determine lung tissue elasticity, as required for ventilation. Lung tissue elasticity maps at 3 months after RT will be compared to those prior to RT, and used to quantify the change in the lung elasticity maps. Reduced lung tissue elasticity is defined in this study as a >6% reduction in expansion when compared to the baseline; the amount of lung tissue showing a >6% reduction is the metric for our primary endpoint, and will be tested for a significant difference between the two arms.

1.2. Secondary Objectives

1. Characterize and correlate temporal changes in lung tissue elasticity with delivered radiation doses to anatomical and functional regions within the thorax.
2. Quantify global changes following radiation therapy (RT) for lung cancer, including those observed from Pulmonary Function Tests (PFTs) and inflammation markers in blood plasma for subjects who voluntary consent to provide their blood. These too will be correlated with the delivered radiation doses to anatomical and functional regions within the thorax, and with the maps of post-radiation therapy changes in lung tissue elasticity.
3. Quantify the repeatability of 4DCT based measures of lung tissue elasticity to demonstrate the changes following radiation therapy are greater than the expected variation from the procedure itself and determine the expected variance in longitudinal studies.

2. BACKGROUND

2.1. Lung Cancer and Current Therapy

In the year 2015, over 221,200 new cases of lung cancer were diagnosed and 158,040 deaths were attributed to this disease.[1] Of these, approximately 13% are small cell lung cancers with the remainder being non-small cell lung cancer.[1] Treatment can involve combinations of surgery, chemotherapy, and radiation therapy (both conventional and hypo-fractionation).[2]

Radiation therapy is typically used for small cell lung cancer and the total dose is typically between 45 and 70 Gy. This depends upon the extent of disease, the number of fractions, and the daily delivery technique (once daily *versus* twice daily). Small cell cancers, however, represent the *minority* of treatments for lung cancer and employ different treatment schema.

Radiation therapy for non-small cell lung cancer is dependent upon operative status of the patient. Those patients treated primarily with surgery have radiation and chemotherapy post-operatively as determined by margin status and extent of disease pathologically.[2] Those with slightly more advanced disease are treated with neoadjuvant concomitant chemoradiotherapy. The pre-operative radiation dose is typically limited to 45-50 Gy, based on the hope that reduction of tumor burden will render the patient operable. Patients

with more advanced non-small cell lung cancer are most commonly treated with definitive high dose combination chemotherapy and radiation, the radiation dose ranging from 60-70 Gy. Finally, an increasing number of patients may have limited disease but poor pulmonary function (limiting their operative status). These patients are being treated with stereotactic radiosurgery (generally 3-5 fractions and total dose from 36-60 Gy). This same approach is being used for a number of other patients with recurrent lung cancer or metastatic disease in the lung.

In conclusion, a majority of patients receive radiation therapy as a component of their lung cancer management and the tolerance to this irradiation is limited by the detrimental impact of that treatment (or its potential) on lung function. While tolerance of lung to radiation is generally considered to be 20 Gy there is little data analyzing the anatomic heterogeneity of lung function in the subject prior to treatment so that the radiation may be tailored to minimize impact on function nor is there any significant data analyzing the impact of radiation therapy across lung function globally that takes into account the biomechanical principles that are critical for lung function.

Radiation Side Effects

Radiation to the tumor and nodal targets (commonly hilar and mediastinal) is complicated by respiratory motion. This requires a larger area of normal lung and mediastinal tissue to be treated to ensure that these targets are within the treatment beams used to deliver the dose. Additionally, lung tumors require radiation doses far in excess of the tolerance of normal lung tissue. Common toxicities include radiation pneumonitis, radiation fibrosis, and ultimately altered respiratory capacity. Dose escalation studies show a clear increase in tumor control with increasing radiation dose for primary lung tumors, but that toxicity also increased with dose. Quantification of lung function after radiotherapy has been limited although recognition of its significance is apparent. Spirometry indices as well as DLCO have been shown to be altered following radiotherapy.

In particular, radiation pneumonitis has been loosely correlated to the fraction of the volume of lung irradiated[3] to doses of 10 – 50 Gy.[4-7] The volume of lung receiving 20 Gy or more has a good correlation with radiation pneumonitis in some studies,[3, 5, 8] but not in others.[9, 10] The mean radiation dose to the lung has also provided conflicting results, showing good[3, 7, 11] and poor correlation between a mean dose > 20 Gy and radiation pneumonitis.[6, 12] All of these analyses ignore two factors we believe to be important: 1) the spatial distribution of pulmonary function within the lung is unlikely to be uniform, so the spatial location of the radiation dose matters, and 2) the changes in lung function may be caused by radiation dose both directly and indirectly, where changes occur in regions of the lung receiving what is currently believed to be “sub toxic” doses due to toxic doses in neighboring tissues. Fundamentally, we do not know the cause of this indirectly produced reduced lung function.

2.2. Preliminary Study and Rationale

The relationship between radiation dose and normal lung tissue toxicity has been thoroughly investigated since CT based planning became commonplace over a decade ago,[6] yet the clear indicators for toxicity remain elusive.[7, 13-20] It has been broadly accepted that radiation dose has a direct effect on treated lung tissue and the lung in the treatment field shows radiographic changes consistent with fibrosis.[21] It is largely

assumed that this is the predominant and in some cases only significant effector of altered lung function despite known changes in inflammatory cells outside the treated area. All current avoidance methods for lung tissue depend on direct dose/volume relationships with treated lung.[6, 16, 22, 23]

The present treatment-planning dosimetry constraints for the lung are based on studies that assume lung tissue is homogeneous in its response to toxicity, irrespective of its location or underlying function. Furthermore, it is well known lung function is not distributed uniformly, especially in diseased lungs.[24, 25] Because most patients with lung cancer have a history of smoking or other lung disease it is clear that a majority of patients will have other underlying lung issues such as chronic obstructive pulmonary disease. This will further exacerbate this anatomically relevant heterogeneity of lung function.

No human studies have investigated the relationships between local lung function, spatial radiation dose distribution, and radiation induced lung function changes. However, rat studies are investigating changes in pulmonary function based on irradiation of different regions of rat lung. Luijk et al. showed structural changes in rat lung were only correlated with changes in breathing rate when irradiating lateral lung regions (shielding the mediastinum),[26] and then that greater lung damage was observed when irradiating the heart [27] while holding mean lung dose and volume of lung irradiated constant. They've also shown irradiation of larger volumes to smaller doses causes greater toxicity than treating smaller volumes to larger doses,[28] a result confirmed by others.[29] A common yet unspecified thread in the rat studies is radiation treatments including the mediastinum caused a greater change in pulmonary function. The reasons for these findings is mechanistically undefined.

[figure not shown]

Figure 2. Planned radiation dose distribution (top) and pulmonary function image after radiation therapy (bottom). Both rows of images display a transverse, sagittal, and coronal cut. The tumor is located in the left lung. Post treatment lung function images show a reduction of pulmonary function in the treatment location, and an additional “streak” of function reduction across the right lung beyond the treated volume. This observation is consistent with non-spatial functional tests in the rat model and never before shown spatially in humans.

endpoints, as the most common approaches rely on subjective and ambiguous endpoints: shortness of breath, pulmonary function tests, blood gases, exercise capacity, and radiographic abnormalities. Functional imaging is being recognized as having the potential to provide biomarkers as objective endpoints. A nearly two decades of research in this area is based on single photon emission computed tomography (SPECT) perfusion scans to quantify functional lung by measuring blood content within the alveolar capillary network.[13, 25, 30-38] Other investigators are pursuing pulmonary function measurement using novel MRI techniques[38-40] including hyperpolarized helium-3 detected MRI.[38, 40-45] These approaches are challenged by limited spatial resolution, motion correction, and accurate image registration with treatment planning CT scans. We have chosen to utilize CT based image-registration methods to compute local lung expansion from respiratory gated 4DCT, and have shown its correlation with ventilation.[46] Others have investigated 4DCT based pulmonary function assessment also finding favorable results.[47-54] CT has several practical advantages over SPECT and MRI as a tool to measure regional lung injury. CT is more readily available, more directly quantitative, has higher spatial and temporal resolution, is easier to perform with RT positioning devices, faster, and less expensive.

Scores of investigators have worked to establish a relationship between radiation dose-volume parameters and pneumonitis.[14, 36, 37, 48, 50-76] The most substantial datasets used to establish the correlation of radiation dose with pulmonary toxicity are from Washington University in Saint Louis and RTOG trial 9311. The statistical model derived from the combined datasets identified greater risk for mean lung dose (MLD), and irradiation of the inferior lung. Unfortunately, two lessons from these results are unused in clinical practice: high doses to normal lung and the anatomic distribution of dose within the lung are relevant. Instead, the clinical RT paradigm for pulmonary toxicity modeling is driven by the dose-volume relationship of lung volume treated.

This proposed clinical trial will elucidate the complex inter-relationship between RT treatment and the resultant changes in pulmonary function. While other groups have hypothesized the value of dose rearrangement to limit lung toxicity, we will carefully apply this information systematically in this prospective clinical trial to demonstrate its impact.

3. PATIENT SELECTION

3.1. Eligibility Criteria

- 3.1.1. Histologic diagnosis of a non-small cell lung cancer or lung metastasis from a solid tumor. One biopsy site is adequate for multiple sites of thoracic disease.
- 3.1.2. Treatment includes localized radiation therapy with or without chemotherapy
- 3.1.3. Age \geq 18 years
- 3.1.4. Karnofsky \geq 60%
- 3.1.5. Not pregnant per radiation oncology standard procedures
- 3.1.6. Ability to understand and the willingness to sign a written informed consent document

3.2. Exclusion Criteria

- 3.2.1. Prior (within last 6 months) or future planned therapeutic surgery for the treatment of the existing lung cancer

- 3.2.2. Prior thoracic radiotherapy
- 3.2.3. Severe COPD defined as disease requiring an inpatient stay for respiratory deterioration within the past 3 months
- 3.2.4. Oxygen dependence of > 2 L/min continuously throughout the day at baseline
- 3.2.5. Known underlying collagen vascular disease or intrinsic lung disease that could complicate expected sequelae of radiation (idiopathic pulmonary fibrosis, Wegener's granulomatosis)
- 3.2.6. Uncontrolled intercurrent illness including, but not limited to ongoing or active infection, symptomatic congestive heart failure, unstable angina pectoris, cardiac arrhythmia, or psychiatric illness/social situations that would limit compliance with study requirements

3.3. Inclusion of Women and Minorities

Female and male patients of all ethnic groups will be eligible for treatment in these protocols.

4. RANDOMIZATION PROCEDURES

Patients may not undergo protocol procedures prior to signing consent. All patients must meet eligibility criteria listed in Section 3 and provide written informed consent. The study coordinator will verify eligibility, assign a case number, and register the patient in the UWCCC ONCORE database after simulation and after all eligibility criteria have been met. Information to be recorded

The following information will be recorded for each subject enrolled:

- Protocol number
- Patient's name and initials
- Patient's medical record number
- Patient demographic data including gender, birth date and race.
- Signed patient consent forms
- HIPAA authorization form

4.1. Randomization between Therapy Arms 1 & 2

Patients will be randomized between two arms. Subjects in the first arm will receive conventional treatment planning as described in sections 5.5.1 through 5.5.3. Subjects in the second arm will also receive treatment plans that meet all the criteria of the first arm, but their treatment plans will include strategies to reduce pulmonary function damage following radiation therapy as described in section 5.5.4. Randomization will be performed by the data management team using a random number generator application (developed by Randomness and Integrity Services Ltd., Dublin, Ireland) that is a web based application that can also run on an Apple iPhone, iPad, or iPod touch running iOS 5.1.1 or later.

Amend 3/15/22

The Hypo-fractionation patient cohort has reached accrual of 60 subjects (30 conventional treatment planning, and 30 optimized planning).

The Conventional Fractionation cohort has accrued 46/60, however the treatment assignment of conventional treatment planning versus optimized planning is unbalanced, with 27 assigned to the standard dose specification planning and 19 assigned to the optimized treatment planning.

Accrual has significantly slowed and we are accruing 1 subject every 4-8 weeks. In light of the extremely low accrual we will assign the next 8 subjects to the optimized treatment plan to balance the study arms to ensure each arm has adequate enrollment for proper statistical analysis. When the arms are balanced, we will proceed with randomization via random.org until one arm reaches 30, then the remaining subjects will be placed in the remaining open arm.

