5. PROCEDURES

Potential subjects will be identified through multidisciplinary lung tumor board, consults, and the radiation oncology clinic. Consent will be obtained prior to initial radiotherapy treatment simulation. One biopsy site is adequate for multiple sites of thoracic disease, as the primary endpoint of the study is the assessment of normal lung tissue response to delivered radiation.

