11. STATISTICAL CONSIDERATIONS

11.1. Study Design/Endpoints

The primary endpoint of this study will be the ratio of the tissue elasticity map following RT to the elasticity map before RT (i.e., the Jacobian ratio of (post RT /pre RT)) calculated from 4DCT at 3 months post-RT. Based on the randomness of our measurement technique, diminished expansion is defined as a Jacobian ratio <0.94 (i.e., less than 94% of the pre-RT value). Data for the analysis will consist of the voxel-specific ratios of tissue elasticity measures from scans being compared. The primary and secondary endpoints at 3, 6, and 12 months post-RT include: (i) the volume of lung where diminished expansion occurs (Jacobian ratio (post RT /pre RT) <0.94), (ii) the volume of lung where expansion is improved (Jacobian ratio (post RT /pre RT) >1.06), (iii) the volume of lung where “meaningful” expansion occurs (Jacobian post-RT > 1.1), and (iv) clinically observed pulmonary toxicity determined by PFT endpoints, and (v) changes in inflammation as determined from blood serum.

Some subjects may have multiple sites of disease treated within the thorax. Since these subjects will be treated at all sites with either the control (Arm 1) or experimental (Arm 2) treatment plan, and since the primary endpoint of the study is the assessment of normal lung tissue response to delivered radiation, these subjects represent a single sample within our analysis.

Power analysis shows the planned enrollment of 60 subjects per cohort will ensure 90% power to detect mean difference of 4% in the lung tissue elasticity (percentage of the lung with a Jacobian ratio post-RT/pre RT < 0.94), based on 6.3% deviation in this measure from 13 subjects in our preliminary data. If the normality assumptions of ANOVA are not satisfied, nonparametric rank-based tests will be used instead. All statistical tests will be two-sided and assessed for significance at the 5% level, and will be performed by the UW-Madison Department of Biostatistics and Medical Informatics.

Update as of 2/3/2021: The statistics are based on 30 subjects reaching the 3 month followup time point. To date 106 have been enrolled but 14 did not complete the 3 month imaging time point. Therefore we are adding numbers to replace those subjects and to allow an additional 5 subjects to ensure we complete the protocol and meet the study objectives.

REFERENCES

1. American Cancer Society. *Cancer Facts & Figures 2015*. Atlanta: American Cancer Society; 2015.

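### The 3/15/22 amendment places at least 8 conventional-fractionation subjects without a random draw, and Section 11 would analyse them as if randomised

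*Combined protocol and SAP*

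**What the plan says.** Section 4.1 opens by saying that patients are randomised between the two arms. The paragraph dated 3/15/22, which is current text, reports the hypofractionation cohort full at 30/30 and the conventional cohort at 46 of 60, with "27 assigned to the standard dose specification planning and 19 assigned to the optimized treatment planning". It adds: "Accrual has significantly slowed and we are accruing 1 subject every 4-8 weeks". It then sets three steps:

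1. "we will assign the next 8 subjects to the optimized treatment plan to balance the study arms". The cohort is not named, but with the other cohort full these must be conventional-fractionation subjects.
2. Once the arms are level, draws via random.org resume.
3. The draws run "until one arm reaches 30, then the remaining subjects will be placed in the remaining open arm".

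On timing, Section 5 says: "Consent will be obtained prior to initial radiotherapy treatment simulation". Section 4 says: "The study coordinator will verify eligibility, assign a case number, and register the patient in the UWCCC ONCORE database after simulation".

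Section 11.1 gives the endpoints, a power statement, ANOVA or rank-based tests, and a two-sided 5% level. Its only update, dated 2/3/2021, precedes the amendment. It says "The statistics are based on 30 subjects reaching the 3 month followup time point" and "To date 106 have been enrolled but 14 did not complete the 3 month imaging time point". Neither Section 11 nor any other section says how subjects placed without a draw will be identified or analysed.

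**The concern.** The primary objective in Section 1.1 is a between-arm difference, and random assignment is what allows that difference to be attributed to the planning method. For the block of 8 that support is missing in two ways.

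- **Foreknowledge.** Consent comes before simulation, and under the amendment staff can know that the next subject gets Arm 2 before approaching the patient. That can affect who is offered the trial and who accepts. The inference is weaker for the final fill, because it requires knowledge of the running arm counts.
- **Calendar time.** The 8 subjects enter consecutively with no Arm 1 subject alongside them in this cohort. Any later change in case mix, or in chemotherapy (left to the treating physician by Section 5.6), loads onto the arm contrast.

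A reader of the results could not tell how far the conclusion depends on these subjects, because the plan does not commit to showing the comparison without them.

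**Working it through.** **Inputs.** Section 11.1: difference 4 points, SD 6.3, two-sided 5%. Section 4.1: 27 and 19 assigned, 46 of 60, one subject per 4-8 weeks. Section 11.1 update: 14 of 106 without 3-month imaging. Assumption where needed: draws are simple 1:1, which the documents do not state.

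**The plan's own power figure.** Section 11.1 states 90% with 60 subjects per cohort. A two-sample t-test gives 67.7% at 30 per arm (one fractionation cohort) and 93.2% at 60 per arm (cohorts pooled). Neither is 90%, which needs 54 per arm. The word cohort is ambiguous, so both scales are shown below. That mismatch is a separate matter and nothing here depends on it.

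**How many are not randomised.**
- Forced block: 27 - 19 = 8, giving 27/27. Places left: 60 - 54 = 6.
- Final fill: with fair draws from 27/27 until one arm reaches 30, the remainder is 1, 2 or 3 subjects with probability 0.375, 0.375 and 0.25. It falls in either arm with equal probability.
- Arm 2, if 46/60 is the relevant count and no one is replaced: 8 to 11 of 30, or 27% to 37%.
- Arm 2, if 46 counts enrolled subjects and non-completion is 14/106 = 13% (assumption): 8 × 92/106 = 6.9, so about 7 of 30 evaluable, or 23%, before any fill.
- Range within the cohort: 7/30 to 11/30, or 23-37%. Pooled over both cohorts: 7/60 to 11/60, or 12-18%.

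**Time without a concurrent control.** 8 × 4 = 32 weeks to 8 × 8 = 64 weeks.

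**What a shift would do.** Suppose outcomes move by D points after the amendment. D is an assumption; the documents give no size. In the largest-fill case Arm 2 gains 11 subjects and Arm 1 gains 3, so the bias in the crude contrast is (11/30 - 3/30)D = 0.27D within the cohort and (8/60)D = 0.13D pooled. The standard error is 6.3 × √(2/30) = 1.63 within the cohort and 6.3 × √(2/60) = 1.15 pooled. The noncentral t gives:

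| D | Bias, cohort | Type I error, cohort | Bias, pooled | Type I error, pooled |
|---|---|---|---|---|
| 1 | 0.27 | 5.3% | 0.13 | 5.2% |
| 2 | 0.53 | 6.2% | 0.27 | 5.6% |
| 4 | 1.07 | 9.9% | 0.53 | 7.5% |

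D = 4 equals the whole target difference, so it is an upper illustration. Had 1:1 draws continued, the expected finish would be 34/26 with 7 new subjects in each arm. The coefficient would then be 7/26 - 7/34 = 0.06.

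**What forced balance gains.** Within-cohort power is 67.7% at 30/30, 66.9% at 34/26, and 66.7% averaged over the possible outcomes of 14 further 1:1 draws. The gain is about 1 point.

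**Power of a randomised-only comparison under the amendment as written.** With the forced and fill subjects removed, the cohort has 27-29 v 22 (58.1-59.5%) or 30 v 19-21 (56.4-59.0%), so about 56-60%. Pooled, it has 57-59 v 52 or 60 v 49-51, giving 90-91%.

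**The case against.** The amendment is openly dated and gives its reason. Its aim is adequate enrolment in each arm under very slow accrual, and power is only part of that. From 27/19, plain 1:1 draws over the 14 remaining places would leave Arm 2 below 30 with probability 97%. Reaching 30 would take about 22 further subjects instead of 14, or 32-64 more weeks. This stands, and it is why the allocation rule itself is a trade-off and not an error.

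Several safeguards also stand. Each subject is compared with their own baseline, scans are duplicated at each time point, and post-treatment scans must be done on one named scanner (Sections 5.3, 5.7.5 and 10.1), which limits measurement drift. Tumour dose and normal-tissue limits are the same in both arms (Sections 5.5.4 and 7), which reduces any incentive to select patients by arm. Neither safeguard rules out a change in who is enrolled or in concurrent care. If the cohorts are pooled, the type I error figures for D = 1 and 2 are close to nominal.

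Three stronger readings are tempting, and the documents do not support them.

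- **That 27/19 is shown to be chance.** The exact binomial p is 0.30, but only if 46 is every randomised conventional-fractionation subject under simple 1:1 draws. If 46 counts evaluable subjects, the split mixes allocation with dropout.
- **That 27% is a floor.** It is not: the enrolled-count reading gives about 7 of 30.
- **That the counts contradict each other.** The 60 + 46 = 106 on 3/15/22 equals the 106 enrolled on 2/3/2021. The rate of one subject per 4-8 weeks describes March 2022, after accrual had slowed; no rate is stated for the period between the two dates. One plausible reading is that 106 - 14 = 92 evaluable subjects plus 14 replacements made 106 evaluable. This is inference, so the basis of the counts needs stating.

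**Conclusion.** The point holds in a limited form. The amendment gives up random assignment for the block of 8 and probably a few more, and Section 11 would treat them as randomised. They would make up about 23-37% of the cohort's Arm 2, or 12-18% pooled, depending on what 46 counts, on replacement and on the fill.

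A reader might infer that the arm contrast is biased. The documents give no evidence of selection or drift, and the type I error figures rest entirely on an assumed shift. For shifts of 1-2 points the effect is small; only a shift as large as the target difference brings the within-cohort error near 10%. The supported conclusion is that the analysis plan leaves this exposure unmeasured although the subjects are traceable through case number and registration, while forced balance gains only about 1 point of power. This should be fixed, and it can be fixed whether or not the slots are already filled.

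**What to change.** Add two or three sentences to Section 11 before analysis:

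1. Flag every subject assigned without a random draw, covering both the forced block and the final fill.
2. Pre-specify a comparison restricted to randomised subjects, reported beside the all-subject analysis.
3. Report the number of non-randomised subjects in each arm.
4. State whether 46 and 60 count enrolled or 3-month-evaluable subjects.

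This needs no extra patients. The randomised-only comparison has lower power (about 56-60% within the cohort, 90-91% pooled), so it should be labelled a sensitivity analysis, and a non-significant result there should not be read as contradicting the main one.

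Optionally, for slots still open, the sponsor may consider returning to concealed random draws. One form is 1:1 with the target of 30 per arm restated, which costs about 1 point of within-cohort power on average if no slot has been filled. The other is draws weighted to Arm 2, which can reach 30/30 but requires enrolment period to be accounted for in the analysis. Either changes the allocation rule again mid-trial, so this is a judgement for the sponsor.
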